8.1 General Design Issues

8.1.1 Summary of Study Design

This is a multicenter, prospective, randomized, controlled, double-blinded Phase 2 study intended to evaluate the safety, PK, and preliminary efficacy of 3K3A-APC following administration of tPA, or mechanical thrombectomy or both, in patients with moderate to severe acute ischemic stroke. The original version of the CRM method proposed enrolling one subject at a time⁵⁵. However, others have shown that the performance of the CRM may be improved by enrolling cohorts instead of a single subject¹. Correspondingly, this study will utilize a modified version of the CRM in order to establish a MTD.

The study will enroll approximately 115 subjects, which includes the planned 88 subjects in groups of four (each cohort will include one placebo and three treated subjects) and the additional placebo subjects who may be enrolled during safety review pauses. While placebo is not needed to determine the MTD, a placebo group has been included in order to conduct secondary analyses to examine for a reduction of pre-clinical tPA/mechanical thrombectomy-related bleeds by central read (it is predicted from studies that treatment reduces thrombolysis-related petechial hemorrhage). Subjects will not be considered part of the intent-to-treat (ITT) cohort until they receive any amount of 3K3A-APC or placebo. For example, 'Early Responders,' subjects whose symptoms resolve between initial randomization and initiation of IMP infusion such that they are no longer eligible (repeat NIHSS <5), will be removed from the study and replaced. At any time if enrollment is so rapid that two consecutive cohorts are awaiting DLT review, the IWRS will randomize any enrolled patients to placebo so as to preserve site-level blinding and trial enrollment momentum. These extra placebo treated subjects will enhance the power to detect a change in bleed rates for 3K3A-APC-treated subjects.

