8.3.2 Secondary Outcome (Bleed Rates)

We also assessed the power of the study to evaluate bleed rates between all treated subjects (collapsed across doses) versus placebo subjects. Previous experience suggests that the MRIdetected bleed rate for tPA-treated subjects should be approximately 30%-40%⁵⁶⁻⁶². Furthermore, it is expected from pre-clinical studies that treatment with APC could lead to a rather dramatic decrease in bleed rates for 3K3A-treated subjects^{31,44,63}. Pre-clinical data suggest that 3K3A-APC could reduce bleeding seen after IV tPA or after mechanical thrombectomy^{44,63}. Thus, it is expected that the study could observe a difference between the groups as substantial as a reduction from a 40% bleed rate among placebo subjects to a lack of observed bleeding in the treated group. However, to assess power over a range of conditions, we computed power for all combinations of the following conditions:

- Placebo group bleed rates of 20%, 30%, & 40%
- 3K3A-APC treated group bleed rates of 0.5%, 5%, & 10%
- Overall sample sizes of 48 (36 treated / 12 control) and 88 (66 treated / 22 control) in
 order to assess power under the scenario where the trial proceeds to the end and under
 the scenario where the study stops early for lack of observing any toxicity at the highest
 dose

Table 6 provides a summary of these power calculations. In general, we find:

- If the original assumptions are correct: We would have very high power (>90%) in either scenario
- If the original assumption regarding the placebo rate is correct, but the treated rate is a bit higher:

We would have very good power (>85%) if the study proceeds to the end. We would have lower, but a still acceptable level of power (>64%) if the study stops due to a lack of observed toxicity after 12 cohorts.

• If the original assumption regarding the treatment rate is correct, but the placebo rate is a bit lower:

We would have decent power (>66%) in either scenario, and very good power (>84%) in the scenario where the study proceeds to the end.

• If both assumptions are wrong (placebo rate lower, treatment rate higher): There is lower power overall, but still reasonable power in a number of settings (such as 30% placebo rate versus 10% treated rate)

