8.5.2 Secondary Objectives

Secondary Outcome #1 (PK Parameters): Based upon analysis of PK data from the Phase I study, a one-compartment IV infusion model will be used and will be parameterized in terms of the primary parameters clearance (CL) and volume of distribution (V). Secondary parameters will include C_{max} , AUC_{0-inf}, and $t_{1/2}$ – and will be calculated from the primary parameters. The actual times of the beginning and end of all 5 infusions and each blood sampling time relative to the first dose will be used in the modeling. All modeling will be done using WinNonlin.

Secondary Outcome #2 (Bleed Rates): To assess tPA/mechanical thrombectomy-related bleed rates across the two groups, all treated subjects (regardless of dose) will be compared to all placebo subjects using a Pearson chi-square test. An additional analysis will compare the bleed rates among placebo subjects and subjects treated at each dose level (assuming a sufficient number of subjects were treated at that level).

Exploratory Outcomes: (Stroke Outcome and Immunogenicity Data): To inform the design of any future Phase III trial, the following exploratory outcomes will be compared at the end of the study. Unless explicitly stated otherwise, the comparisons will be conducted first comparing all treated subjects (regardless of dose) versus all placebo subjects, and then comparing all subjects receiving the dose selected as the MTD versus all placebo subjects.

• The mean bleeding (hemorrhage and microbleeds) volume at Day 30 will be compared using a linear regression model. Median and categorical volumes (based upon quartiles) will be compared.

- Rates of subarachnoid hemorrhage in subjects who receive mechanical thrombectomy will be compared; all mechanical thrombectomy 3K3A-APC-treated subjects (regardless of dose) will be compared to all placebo subjects using a Pearson chi-square test.
- The 7-day NIHSS mean scores will be compared using a Kruskal-Wallis test.
- The change from Baseline NIHSS to 7-day NIHSS will be compared using a linear regression model, with baseline NIHSS score as a covariate.
- The 90-day mRS will be compared using a Pearson chi-square test.
- The mean infarct volume at 90 days (MRI, or CT if unable to obtain MRI) will be compared using a linear regression model. Median and categorical infarct volumes (based upon quartiles) will be compared.
- The 90-day BI will be compared using a Kruskal-Wallis test.

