8.3 Exploratory Outcomes

A number of additional exploratory analyses are also planned, but will not be included as part of the FSR. Unless explicitly stated otherwise, the comparisons will be conducted first comparing all treated subjects (regardless of dose) versus all placebo subjects, and then comparing each dose individually. These exploratory analyses include, but are not limited to the analyses described below.

- This study will include additional bleeding outcome data of interest. While the sample size is likely too small to observe meaningful treatment effects, the data allow confirmation that outcomes in this trial resemble previously published trials. Corresponding, the following exploratory analyses will be considered:
 - Evaluating the effect of 3K3A-APC on the volume of tPA/mechanical thrombectomy related hemorrhage in the brain as determined by MRI at Day 30
 - Evaluating the effect of 3K3A-APC on the incidence of subarachnoid hemorrhage in subjects who receive mechanical thrombectomy
 - Evaluating the effect of 3K3A-APC on the incidence of hemorrhage at Day 7.
- To inform the design of any future phase II/III trial, the study will also include outcome data typically collected in all stroke trials, as well as sample collection to assess the immunogenic potential of 3K3A-APC. Correspondingly, additional exploratory analyses will include comparisons across groups for:
 - Day 7 National Institute of Health Stroke Scale (NIHSS) Scores
 - Change from Baseline NIHSS to Day 7 NIHSS
 - Day 90 Modified Rankin Scale (mRS)
 - Infarct Volume at 90 Days (MRI, or CT if unable to obtain MRI):
 - Day 90 Barthel Index (BI) Scores
 - The relationship between the 7-day NIHSS score and the 90-day mRS will be examined using a linear regression model. The degree of fit and the R-square will be determined, and the model will be used to assess the potential for using the 7-day outcome in subsequent studies.
 - Pre-Dose 1, Day 14, and Day 30 Anti-Drug Antibody Samples: The tendency of the drug to induce an immunogenic response in patients will be assessed.

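### The 90-day mRS is assigned a Pearson chi-square test with no scale stated; an ordinal analysis would give more power and a usable effect estimate

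*Protocol*

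**What the plan says.** Protocol 8.5.2, in its list of exploratory outcomes, gives one sentence to this endpoint: "The 90-day mRS will be compared using a Pearson chi-square test". Neither the number of categories nor a cut-point is given. The same list treats two other ordered scales differently: "The 7-day NIHSS mean scores will be compared using a Kruskal-Wallis test" and "The 90-day BI will be compared using a Kruskal-Wallis test". The default contrast is "first comparing all treated subjects (regardless of dose) versus all placebo subjects", followed by the MTD dose against placebo.

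SAP 8.3 lists "Day 90 Modified Rankin Scale (mRS") among the comparisons across groups and attaches no test, so it neither replaces nor clarifies the protocol's choice. It also sets the status of these analyses: "A number of additional exploratory analyses are also planned, but will not be included as part of the FSR".

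Protocol 8.5.2 says the exploratory comparisons are meant to inform a future Phase III trial; SAP 8.3 says phase II/III. Protocol 8.2.2 concedes that the sample is too small to show meaningful treatment effects on these outcomes. No mRS power, effect size or distribution is stated.

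**The concern.** The mRS runs from 0 (no symptoms) to 6 (death), and its information lies in the order. A Pearson test on a 2 x 7 table has up to 6 degrees of freedom and gives the same answer however the columns are rearranged. It spreads its power over patterns nobody expects and returns a p-value with no direction, estimate or interval. A team planning the next trial needs the size of the shift and its uncertainty, and this test supplies neither.

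If a dichotomy was meant, the plan leaves the cut-point open, so it could be chosen after the data are seen. Either way one sentence is missing. What is at stake is the planning value of the mRS data; the MTD and the bleed-rate comparison do not depend on it.

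**Working it through.** **Inputs from the documents.** Group sizes are 66 treated / 22 placebo for full cohorts and 36 / 12 for early stopping (Protocol 8.3.2). "The study will enroll approximately 115 subjects" (Protocol 8.1.1); if all 22 cohorts fill and every additional subject is placebo, that gives 115 - 66 = 49 placebo. Protocol Table 1 gives mRS 0-2 and mortality for earlier thrombectomy trials, but no seven-level distribution.

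**Assumptions.** Two-sided alpha 0.05; a proportional-odds shift with common OR 1.5 to 4; control distributions with mRS 0-2 / mortality of 29% / 19%, 40% / 15% and 53% / 10%, all within the Table 1 ranges. A worked example uses control probabilities 0.12, 0.17, 0.16, 0.15, 0.16, 0.09, 0.15 for mRS 0 to 6 (45% mRS 0-2, 15% dead).

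**Method check.** The plan has no mRS figure to reproduce. Its only chi-square power table is Table 6 (bleed rates). With power = Phi[(|p1 - p2| - 1.96 se0) / se1], where se0 is the pooled and se1 the unpooled standard error, 40% against 10% at 22/66 gives se0 = sqrt(0.175 x 0.825 x (1/22 + 1/66)) = 0.0935 and se1 = sqrt(0.24/22 + 0.09/66) = 0.1108. Then Phi[(0.30 - 0.1833)/0.1108] = Phi(1.053) = 85.4%, against 85% stated. All 18 cells agree within 2 points.

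**The shift at OR 2.** Each cumulative control probability c becomes 2c/(1 + c). So mRS 0-2 moves from 0.45 to 0.90/1.45 = 0.621, and death from 0.15 to 1 - 1.70/1.85 = 0.081.

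**Seven-level Pearson against rank test.** Simulated, 40,000 trials per setting, range over the three control distributions:

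| OR | 66/22: Pearson vs rank | ratio | 66/49: Pearson vs rank | ratio |
|---|---|---|---|---|
| 1.5 | 7-10% vs 15% | 0.48-0.65 | 11% vs 23% | 0.47-0.50 |
| 2 | 16-21% vs 35% | 0.46-0.59 | 27-29% vs 54-55% | 0.49-0.53 |
| 2.5 | 28-35% vs 55% | 0.51-0.64 | 48-49% vs 78% | 0.61-0.63 |
| 3 | 42-48% vs 70% | 0.59-0.68 | 66-67% vs 90% | 0.73-0.74 |
| 4 | 64-69% vs 88% | 0.73-0.79 | 88% vs 98% | 0.89-0.90 |

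The worked example at OR 2 gives about 29% against 55% at 66/49 and 19% against 35% at 66/22. An analytic check at 66/49 agrees: the noncentrality (66 x 49 / 115) x sum[(p1 - p0)^2 / pbar] is 4.27, which on 6 df gives 28.7%. At 36/12 the ratio is 0.44-0.70 across the ORs. Type I error is about 4-5% for the seven-level test and 5% for the rank test.

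**Dichotomy, mRS 0-2 against 3-6.** At OR 2 power is 26-30% against 35% for the rank test (66/22), and 42-45% against 54-55% (66/49). Over all sizes and ORs the ratio is 0.74-0.97, a relative loss of 1 - 0.97 = 3% to 1 - 0.74 = 26%.

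**Expected counts, worked example, no effect.** With 22 placebo subjects, all seven placebo cells fall below 5 (largest 22 x 0.17 = 3.7), so 7 of 14. With 49, only one does (49 x 0.09 = 4.4). The Fisher fallback in SAP 8.2 is written for the bleeding comparisons only.

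**The case against.** The strongest reply is that a seven-level test is only something a reader might infer. Elsewhere in Protocol 8.5.2 the Pearson test is used for yes/no outcomes, the multi-level scales get Kruskal-Wallis, and Table 1 summarises earlier trials as mRS 0-2. A 2 x 2 test is therefore plausible; it has a direction, and its loss of power is modest. This stands as a limit on the claim. It does not remove the point, because no cut-point is set for analysis anywhere, and the same section regresses the 90-day mRS on the 7-day NIHSS as a graded score.

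A reader might also infer that power is halved whatever the effect. The documents give no mRS effect size or distribution, and the calculation supports halving only for seven levels and an OR of about 1.5 to 2. A proportional-odds shift is also the alternative that favours a rank test. Nor do sparse cells make the test invalid: the simulated Type I error does not exceed the nominal level.

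Finally, the endpoint is exploratory, outside the final study report, and carries no power claim. The SAP's list is expressly not exhaustive, so an ordinal model is not excluded, and a common OR could be computed later from the recorded scores. Kruskal-Wallis would not supply one either. All of this stands and keeps the point small. An estimate specified in advance is still better for planning than one chosen afterwards.

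**Conclusion.** The point holds in a limited form. The protocol names a Pearson chi-square without a scale, its neighbours get rank tests, and the SAP is silent. An ordinal analysis is better on either reading. On seven levels the named test has about half the power of a rank test at an assumed OR near 2 and keeps about 0.6 to 0.9 of it at OR 3 to 4 (66/22 and 66/49). On an mRS 0-2 dichotomy the relative loss is about 3-26%, with the cut-point open.

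These sizes rest on assumed control distributions, an assumed proportional-odds shift and two-sided alpha 0.05. Even the rank test has only about 35% (66/22) to 55% (66/49) power at OR 2, so changing the test does not make this an adequately powered comparison. The main gain is an effect estimate with an interval. A reader might infer that a trial conclusion is at risk; the documents do not support that, because no primary or secondary conclusion uses the mRS test.

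**What to change.** Make the same change in Protocol 8.5.2 and SAP 8.3; changing only the SAP would leave the two in conflict. State that the 90-day mRS is analysed on all seven levels, 0 to 6 with death scored 6, by a proportional-odds model adjusted for baseline NIHSS and recanalization therapy. Say which baseline NIHSS is used, since SAP section 5 tabulates more than one. Report the common OR with its 95% CI and the mRS distribution by group, and name the Wilcoxon test as fallback.

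The covariates are already collected, so no new data, visits or subjects are needed. The cost is one sentence in each document, with the sponsor and CIRB approval that Protocol 6.4.6 requires for an amendment, settled before outcomes are compared by group. The drawback is reliance on the proportional-odds assumption, which this sample can check only roughly. The Wilcoxon fallback avoids that model but gives no common OR.

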6.4.3 Treatment History

All treatments, including administration of tPA or use of thrombectomy devices, will be recorded in the subject's medical record (source documentation) and in the eCRF. Baseline medications will be recorded 3 days prior to tPA or mechanical thrombectomy through just prior to first administration of study drug.

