5. PRELIMINARY TABULATIONS

All subjects who provide informed consent will be accounted for in this study. Regularly generated enrollment reports will describe:

- Number of subjects consented, eligible, and randomized by site
- Ongoing study status of all randomized subjects
- Reasons for ineligibility
- Protocol deviations
- Early study completers

Subject data will also be summarized by treatment group (combined 3K3A-APC vs. placebo & individual dose groups vs. placebo) with respect to important demographic characteristics. Distribution of categorical variables will be tabulated by treatment group. Continuous variables will be summarized as mean, standard deviation, minimum, and maximum by treatment group and overall. Variables to be collected will include:

- Demographic Characteristics and Baseline Measurements
 - Gender
 - Race
 - Ethnicity
 - Age
 - Years of Education
 - Hand Preference
 - Height (cm)
 - Platelet Count
 - History of Diabetes
 - History of Hypertension
- Baseline Stroke Characteristics & Timeline
 - NIHSS Prior to Recanalization Therapy
 - NIHSS Eligibility
 - Recanalization Therapy
 - mRS
 - Time from Stroke Onset to First Therapy
 - If tPA Only, Time from Stroke Onset to tPA Initiation
 - If IAT Only, Time from Stroke Onset to First Skin Puncture

- If IAT & tPA, Time from Stroke Onset to tPA Initiation or First Skin Puncture (Whichever Occurred First)

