8.2 Analysis of Hemorrhage Rates

The incidence of hemorrhage, overall and by type (as defined above), will be summarized in a table similar to the one below:

Table 3. Bleeding Rates

Type	Total (N = XX)	Treated (N = XX)	Placebo (N = XX)	P-Value
Hemorrhage (Volume > 0.06 mL)	XX (%)	XX (%)	XX (%)	X.XX
(Volume > 0 mL)	XX (%)	XX (%)	XX (%)	X.XX
(Volume > 0.5 mL)	XX (%)	XX (%)	XX (%)	X.XX
(Volume > 1.8 mL)	XX (%)	XX (%)	XX (%)	X.XX
Microbleeds	XX (%)	XX (%)	XX (%)	X.XX

To assess tPA/mechanical thrombectomy-related hemorrhage rates across the two groups, all treated subjects (regardless of dose) will be compared to placebo subjects using a Pearson chi-square test. This test will assess the null hypothesis that there is no relationship between treatment group assignment and hemorrhage rates versus the alternative hypothesis that the groups differ with respect to hemorrhage rates. If any of the expected cell counts are too small to justify the use of the Pearson chi-square test, Fisher’s Exact test will be used instead.

If we fail to reject H_0 , then we will conclude that there is no significant difference between the placebo and 3K3A-APC groups. If H_0 is rejected, then we will conclude that the two groups differ with respect to hemorrhage rates – with the direction of the difference indicating which group has an increased (decreased) risk of hemorrhage. For example, if H_0 is rejected and the hemorrhage rate is lower in the 3K3A-APC group, then we will conclude that participants in the 3K3A-APC group have a significantly lower rate of hemorrhage than participants in the placebo group.

An additional analysis will compare the total hemorrhage rates among placebo subjects and subjects treated at each dose level (assuming a sufficient number of subjects were treated at that level). Again, if the assumptions of the Pearson chi-square test are not met, then Fisher’s exact test will be used instead.

All prior analyses will be repeated to compare the groups with respect to incidence of microbleeds at Day 30.

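### The Day 90 infarct-volume and Barthel Index comparisons name no adjustment for baseline severity or recanalization type, although both are collected

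*Protocol*

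**What the plan says.** Protocol 8.5.2 plans the Day 90 infarct-volume comparison as follows: "The mean infarct volume at 90 days (MRI, or CT if unable to obtain MRI) will be compared using a linear regression model". No covariate is attached. For the Barthel Index it says: "The 90-day BI will be compared using a Kruskal-Wallis test". The contrast is the change in NIHSS from baseline to Day 7, which is modelled "with baseline NIHSS score as a covariate". That is the only covariate named in any group comparison of a secondary or exploratory outcome.

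For the Day 30 bleed rate, Protocol 8.5.2 says that "all treated subjects (regardless of dose) will be compared to all placebo subjects using a Pearson chi-square test". SAP 8.2 repeats this and adds Fisher's exact test where expected counts are small. SAP 8.3 says that "additional exploratory analyses will include comparisons across groups for" a list of outcomes. Infarct volume and Barthel Index are on the list, with no model given for either.

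The baseline information exists. SAP 5 tabulates "NIHSS Prior to Recanalization Therapy", a separate eligibility NIHSS, and recanalization therapy. Protocol 6.4.3 says: "All treatments, including administration of tPA or use of thrombectomy devices, will be recorded in the subject's medical record", and also in the eCRF. SAP 3.2 includes infarct volume at baseline in the central read. Protocol 4.4.4 and SAP 4 describe 3:1 allocation and name no stratification factor.

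**The concern.** Eligibility requires an NIHSS of at least 5 with no upper limit, and the trial mixes tPA alone, thrombectomy alone and both, so case mix can vary widely. The protocol itself treats early NIHSS as a candidate predictor of the 90-day mRS. Table 1 of the protocol shows functional outcome differing between thrombectomy and control arms in several trials. Both factors are therefore plausibly prognostic for infarct volume and Barthel Index.

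Protocol 8.5.2 says that these exploratory comparisons are meant to inform a later trial. Without adjustment, the estimates carry residual variation that a baseline value could remove, and any chance difference in severity or treatment type between arms passes straight into the estimated effect. Leaving the model open also allows covariates to be chosen after the data are seen.

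**Working it through.** **Inputs.** 66 treated and 22 placebo, or 36 and 12 after an early stop (Protocol 8.3.2). About 115 subjects in total (Protocol 8.1.1), so 115 − 88 = 27 extra placebo subjects and 22 + 27 = 49 placebo. Significance level 0.05 (SAP 6), two-sided by the alternative stated in SAP 8.2. The correlation r between baseline NIHSS and infarct volume is assumed; the documents give neither a correlation nor a standard deviation.

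**1. The plan's own figure.** Table 6 gives the power of the unadjusted bleed-rate test. With the pooled-variance chi-square formula, at 40% v 10% and 22:66:
- pooled rate = (0.4×22 + 0.1×66)/88 = 0.175
- null SE = √(0.175×0.825×(1/66 + 1/22)) = 0.0935
- alternative SE = √(0.4×0.6/22 + 0.1×0.9/66) = 0.1108
- z = (0.30 − 1.96×0.0935)/0.1108 = 1.05, power 85%, as printed.

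All 18 cells reproduce within 1 point.

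**2. Precision for infarct volume.** SE ratio = √(1 − r²). Equivalent sample size = 1/(1 − r²). The difference detectable with 80% power, in SD units, is (1.96 + 0.842) × √(1/n_t + 1/n_c) × √(1 − r²).

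| Assumed r | SE ratio | Equivalent sample size | Detectable, 66:22 | Detectable, 66:49 |
|---|---|---|---|---|
| unadjusted | 1.00 | ×1.00 | 0.69 | 0.53 |
| 0.3 | 0.95 | ×1.10 | 0.66 | 0.50 |
| 0.5 | 0.87 | ×1.33 | 0.60 | 0.46 |
| 0.6 | 0.80 | ×1.56 | 0.55 | 0.42 |

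**3. Chance imbalance.** For a factor with 50% prevalence (assumed), the SD of the difference in prevalence is √(0.25×(1/n_t + 1/n_c)):
- 66:22: 0.123, 95% range ±24 points
- 66:49: 0.094, 95% range ±18.5 points
- 36:12: 0.167, 95% range ±33 points.

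An imbalance above 20 points has probability about 10% at 66:22 and 3% at 66:49.

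**4. Effect of an imbalance on infarct volume.** For a covariate out of balance by 1.96 SE, the unadjusted difference shifts by r × 1.96 × √(1/n_t + 1/n_c) outcome SDs. At r = 0.5 this is 0.5×1.96×0.246 = 0.24 SD at 66:22, and 0.5×1.96×0.189 = 0.19 SD at 66:49. Given such an imbalance, the type I error of the unadjusted test is about 13%. Averaged over all randomizations it is about 5%.

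**5. Bleed rate.** Pearson chi-square was compared by simulation with a Cochran-Mantel-Haenszel test over four strata (severity by recanalization type, each 50% prevalent, prognostic odds ratios 2, 3 and 5, all assumed; 8,000 runs per cell). Over four pairs of rates, stratification changed power by −0.6 to +5.7 points at 66:22 and −2.6 to +2.5 points at 66:49. If neither factor is prognostic, the largest loss was about 4 points (81.6% to 77.4%, for 30% v 10% at 66:49). Stratifying by recanalization type alone uses two strata, so these figures are indicative.

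**The case against.** A reader might infer that the bleed-rate test, the key secondary comparison, also wastes precision. The simulation does not support that: at the planned size of about 66:49 the power change is close to zero and sometimes negative. Even a bad case is modest there. A 2-SD imbalance in a factor that moves the bleed rate by 20 points (assumed) shifts the difference by 2×12.3×0.20 = 4.9 points at 66:22, or 2×9.4×0.20 = 3.8 at 66:49. The standard errors of the difference at 10% v 30% are 10.4 and 7.5 points, so the shift is about half a standard error.

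A reader might also infer that large imbalances will be present. They are possible, not established, and SAP 5 would reveal them by tabulating both factors by arm. The absence of stratification is itself inferred: Protocol 8.1.2 refers to a scheme held by the coordinating center that is not reproduced.

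Nor do the documents show a decision against adjustment for infarct volume. A linear regression can take covariates, and SAP 8.3 leaves the list of analyses open. The defect is an unspecified model.

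Finally, the protocol says the sample is too small to show meaningful effects on the exploratory outcomes, and SAP 8.3 keeps them out of the final study report. All of this stands, and it limits the point. It does not remove it: the Kruskal-Wallis test takes no covariates, the regression names none, and the protocol adjusts NIHSS change for baseline while leaving these two outcomes without any stated adjustment.

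**Conclusion.** The point holds for infarct volume and Barthel Index as a modest improvement. For infarct volume the standard error would fall by about 5% to 20% if r lies between 0.3 and 0.6; that range is an assumption, and a weaker correlation would give less. No figure is offered for Barthel Index, because the documents give nothing to base one on. Adjustment also protects against chance imbalance, which at these sizes can reach roughly 18 to 24 points on a common binary factor.

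For the bleed rate, the case is only for a sensitivity analysis against differing case mix. One source is not pure chance: about 27 placebo subjects are expected to enter during review pauses, when no one is allocated to active drug, so their case mix may differ systematically. The planned unadjusted tests remain valid on average over randomizations.

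**What to change.** In SAP 8.3, with matching wording in Protocol 8.5.2:

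- **Infarct volume.** Name as covariates the NIHSS used for eligibility at randomization, and recanalization type (tPA only v thrombectomy with or without tPA). SAP 5 lists two NIHSS values, so say which is meant. Define recanalization type as known or planned at randomization: the first infusion is timed from tPA completion or arterial puncture, whichever is sooner, so the text does not exclude a thrombectomy that starts after dosing. Add central-read baseline infarct volume where measurable, in a second model so that the first loses no subjects.
- **Barthel Index.** Use a proportional-odds or rank-based model with the same two covariates.

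In SAP 8.2, keep the chi-square test with its Fisher fallback as primary, and add a Mantel-Haenszel estimate stratified by recanalization type, labelled as a sensitivity analysis. Few bleeds are expected (0.10×66 + 0.30×22 ≈ 13 at 10% v 30%), so do not add many factors.

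The cost is a short wording change in both documents and slightly more analysis, with no new visits or scans. The documents do not say whether the planned recanalization type is captured at randomization; if it is not, derive it from the recorded treatments and their times. Settle the wording before unblinding.

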6. ANALYSIS POPULATIONS

Since the primary objective aims to estimate a maximum tolerated dose, no formal testing will be involved. All analyses to address the key secondary objectives will be conducted at the 0.05 significance level. The analysis population of interest will differ depending on the objectives of any particular analysis.

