6.3. Secondary Bleed Rate (Hemorrhage & Microbleeds) Analysis

The secondary bleeding analysis will be based on the results of the Day 30 MRI scans. Correspondingly, the analysis population for this secondary analysis will include all subjects who had a Day 30 scan collected.

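### The 90-day Barthel Index comparison has no rule for subjects who died, so by default it runs in survivors only and can point the wrong way if mortality differs between arms

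*Protocol*

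**What the plan says.** Protocol 8.5.2 lists the exploratory analyses. For the Barthel Index (BI), "The 90-day BI will be compared using a Kruskal-Wallis test". The early neurological score gets the same kind of rank test: "The 7-day NIHSS mean scores will be compared using a Kruskal-Wallis test". Its movement since entry is handled by regression instead, with this wording: "The change from Baseline NIHSS to 7-day NIHSS will be compared using a linear regression model, with baseline NIHSS score as a covariate". Lesion size is also handled by regression: "The mean infarct volume at 90 days (MRI, or CT if unable to obtain MRI) will be compared using a linear regression model". For infarct volume the only fallback is CT in place of MRI. Medians and quartile categories are also to be compared.

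On who is compared, the Protocol says that "the comparisons will be conducted first comparing all treated subjects (regardless of dose) versus all placebo subjects", followed by the MTD dose against placebo. SAP 8.3 has "comparing all treated subjects (regardless of dose) versus all placebo subjects, and then comparing each dose individually", and names no test for the BI.

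SAP section 6 states that "The analysis population of interest will differ depending on the objectives of any particular analysis". It then defines populations for the CRM, PK, Day 30 bleeding and safety analyses, and none for the exploratory outcomes. The one explicit observed-data rule for an imaging outcome is for Day 30 bleeding: "the analysis population for this secondary analysis will include all subjects who had a Day 30 scan collected".

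Neither document gives a score, rank or imputation rule for death in the BI, NIHSS or infarct-volume comparisons. SAP 10.8 compares deaths between arms as a separate safety outcome.

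**The concern.** The stated comparison is of all subjects, but it cannot be carried out as stated because a subject who died has no BI. Unless a rule is added, the software drops these subjects and the test becomes a comparison of survivors. Survival to Day 90 is determined after randomisation and may depend on treatment, so the two groups of survivors need not be comparable.

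Suppose the drug keeps alive some subjects who would have died, and they survive with very low scores. They then enter the drug arm's BI distribution at the bottom, while their placebo counterparts disappear. A benefit shows up as worse function. A drug that raises mortality would be flattered in the same way.

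The Protocol wants these comparisons to inform a Phase III design, and such planning uses the direction and size of the estimate.

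**Working it through.** There is no figure of the plan's own to reproduce: the documents give no effect size, power or expected mortality for the BI. The check is therefore of the text and of the mechanism.

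**Text.** Protocol 8.5.2, SAP 8.3 and SAP 6 to 6.4 were read for a rule on death, missing values or population for the BI. There is none.

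**Inputs for the illustration**
- Arm sizes: 66 treated and 22 placebo in the cohorts (Protocol 8.3.2), about 115 subjects in total (Protocol synopsis). Taking all 115 − 88 = 27 additional subjects as placebo gives 22 + 27 = 49. This is an assumption.
- Mortality: 9% drug and 18% placebo, assumed. For scale, Protocol Table 1 shows 9% to 22% across the arms of five thrombectomy trials. It does not state a time point.
- Subjects lost: 0.09 × 66 ≈ 6 on drug and 0.18 × 49 ≈ 9 on placebo.
- Model: each subject has one latent severity rank, distributed identically in both arms. The worst fraction of each arm dies. The drug only keeps some of that fraction alive, with the lowest scores.

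**Formulas.** Let m_T and m_C be mortality on drug and placebo, with m_T ≤ m_C. Ties count one half.
- Survivors only: P(drug subject does better) = 0.5 × (1 − m_C)/(1 − m_T). A drug survivor from the saved fraction loses to every placebo survivor; any other drug survivor wins half the time.
- Deaths ranked worst: P = 0.5·m_T·m_C + (1 − m_T)·m_C + 0.5·(1 − m_C)² = 0.5 + 0.5·m_C·(m_C − m_T).

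**Numbers for 9% against 18%**
- Survivors only: 0.5 × 0.82/0.91 = 0.45.
- Deaths ranked worst: 0.5 + 0.5 × 0.18 × 0.09 = 0.508, or 0.51.

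| Mortality, drug / placebo | Survivors only | Deaths ranked worst |
|---|---|---|
| 9% / 18% (assumed) | 0.45 | 0.51 |
| 10.4% / 19.0% (a Table 1 pair) | 0.5 × 0.810/0.896 = 0.45 | 0.51 |
| 9.2% / 12.4% (a Table 1 pair) | 0.5 × 0.876/0.908 = 0.48 | 0.50 |
| 15% / 15% (assumed) | 0.50 | 0.50 |

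The Table 1 pairs are device against control. They are used only to vary the size of the gap, not as predictions for this drug.

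**Simulation under the same model** (BI in steps of 5, two-sided 0.05 assumed because no level is stated for exploratory outcomes). At 9% against 18%, the survivors-only test rejects in about 12% of trials, almost always against the drug, and the estimate has the wrong sign in about 80%. With deaths ranked worst it rejects in about 5%. At equal mortality both reject in about 5%.

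**Another shape for the BI.** Here saved subjects have BI 0 to 20, with mortality of 10% on drug and 20% on placebo and arms of 66 and 49. The mean difference, drug minus placebo, is −6.4 points in survivors and +1.6 with deaths scored 0. At 9.2% against 12.4% it is −1.9 and +0.7.

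**The case against.** The strongest reply is that the consequence is small. The outcomes are exploratory, Protocol 8.2.2 says that the sample is too small to show meaningful effects, SAP 8.3 keeps them out of the final study report, and SAP 10.8 compares deaths by arm, so a reader of the BI result could see an imbalance. All of that stands and sets the severity. It does not remove the point: a separate table of deaths does not correct a biased BI estimate, and an estimate used for planning matters even without a significant test.

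The illustration also builds in its own direction. It needs a mortality difference, and it needs the extra survivors to be the most disabled. The Table 1 contrasts are of devices in large vessel occlusion, whereas this trial also enrols subjects given tPA alone. One pair is nearly equal (21% and 22%) and one is reversed (18.4% and 15.5%). This stands too, so the figures are conditional.

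Three stronger readings are tempting and are not supported.
- A reader might infer that the plan prescribes a survivors-only analysis. It does not. It promises all subjects and is silent on deaths; survivors-only is the default that follows.
- A reader might infer that any life-saving drug would look harmful. That needs both conditions above.
- A reader might infer the same size of problem for Day 7 NIHSS and infarct volume. The gap in wording is the same, but the documents give no Day 7 death rate, and no magnitude can be shown for either outcome. Ranking deaths worst on infarct volume would also mix survival with an anatomical measure, which is debatable.

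**Conclusion.** The point holds for the 90-day BI as a gap in the plan with a foreseeable default. Neither document tells the analyst what to do with a subject who died, and the named test run on available scores omits those subjects. If mortality differs and the extra survivors are severely disabled, the result is biased against the arm with fewer deaths. Under the assumed 9% against 18%, the probability of doing better is 0.45 in survivors and 0.51 with deaths ranked worst. The bias shrinks with the mortality gap and vanishes at equal mortality.

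For Day 7 NIHSS the effect is likely smaller, since fewer deaths will have occurred by then, and it cannot be sized from the documents. Because the outcomes are exploratory and unpowered, this is a desirable clarification rather than a threat to the trial's main conclusions.

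**What to change.** Before unblinding, state in Protocol 8.5.2 and SAP 8.3:
- The population for exploratory outcomes is all dosed subjects.
- A subject who died before the Day 90 assessment takes the worst rank, below a score of 0, in the BI Kruskal-Wallis test. This applies to the pooled and the dose-level comparisons. SAP 8.3 should name the test.
- A survivors-only BI analysis, labelled as such, is reported alongside.
- The same worst-rank rule may be used for the Day 7 NIHSS rank test. The assigned rank must not enter the NIHSS regressions, that is, change from baseline and Day 7 NIHSS against Day 90 mRS.
- Infarct volume stays as planned, labelled as survivors-only, with the number of deaths per arm beside it.

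Also confirm that vital status is recorded to Day 90. SAE collection ends at Day 30 (Protocol 6.1; SAP 10.2). Protocol 4.4.4 follows dosed subjects to the end of the study, but the plan should say where a later death is captured.

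The cost is a few sentences in two documents. No extra subjects are needed, and the BI test is the one already planned. The BI result becomes a comparison of survival plus function and must be reported as such.
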